7.4. Dosage Modification

Not applicable.

7.5. Preparation/Handling/Storage/Accountability

All investigational product (used and partially used) will be returned to the sponsor or destroyed at site level with the sponsor's written approval. In some cases, sites may destroy the material if, during the investigative site selection, the evaluator has verified and documented that the site has appropriate facilities and written procedures to dispose of clinical trial materials.

Follow storage and handling instructions on the investigational product packaging.

7.6. Treatment Compliance

Patient compliance with study medication will be assessed at each visit during the treatment period (Visit 4 through Visit 28) by counting returned tablets.

A patient will be considered significantly noncompliant if he or she misses more than 20% of the prescribed doses of investigational product during the study, unless the patient's investigational product is withheld by the investigator for safety reasons. Similarly, a patient will be considered significantly noncompliant if he or she is judged by the investigator to have intentionally or repeatedly taken 20% more than the prescribed amount of medication during the study.

Patients will be counseled by study staff on the importance of taking the investigational product as prescribed, as appropriate.

Patients' compliance will be further defined in the statistical analysis plan (SAP).

7.7. Concomitant Therapy

All concomitant medication, whether prescription or over the counter, used at baseline and/or during the course of the study, must be recorded on the Concomitant Medication electronic case report form (eCRF). Patients will be instructed to consult the investigator or other appropriate study personnel at the site before taking any new medications or supplements during the study. For AD therapies permitted as part of rescue therapy, see Section 7.7.5.

7.7.1. Permitted Medications and Procedures

Treatment with concomitant AD therapies during the study is permitted only as described below.

- Daily use of emollients is required as background treatment up to Week 104. After Week 104, the continued use of emollients is encouraged. Moisturizers with antipruritics or antiseptics are not permitted up to Week 104. If daily applications are missed, it will not be considered a protocol violation. Emollients will not be supplied by the sponsor, unless required by local regulations.
 - Patients should not apply emollients on the day of their study visit prior to the procedures to allow for adequate assessment of skin dryness.
- Background TCS therapy (e.g., triamcinolone 0.1% cream and/or hydrocortisone 2.5% ointment) are to be used on active lesions in Periods 2 and 3, as described in Section 7.7.2.
- High- or ultra-high-potency TCS are only permitted as rescue therapy as described in Section 7.7.5 (Rescue Therapy).
- During Period 4, concomitant use of TCS may be continued, as directed by the investigator, as per clinical practice.
- TCIs (e.g., tacrolimus and pimecrolimus), or topical PDE-4 inhibitor (i.e., crisaborole, where approved) are permitted in place of TCS on areas where application of TCS is considered inappropriate by the investigator; use should be limited to problem areas (e.g., face, neck, skin folds, genital areas, etc.) as described in Section 7.7.2.
- Phototherapy, including therapeutic phototherapy (psoralen and ultraviolet A, ultraviolet B, excimer laser), is permitted as rescue therapy in Periods 2 to 4 (see Section 7.7.5, Rescue Therapy); however, it requires a temporary interruption of investigational product (see Section 8.1.1).

In addition, the following therapies are permitted during the study:

- intranasal or inhaled steroids
- leukotriene inhibitors (e.g., montelukast [Singulair], zafirlukast [Accolate], and zileuton [Zyflo])
- topical anesthetics and topical and systemic anti-infective medications
- cyclosporine ophthalmic emulsion (e.g., Restasis)
- nonlive seasonal vaccinations and/or emergency vaccination, such as rabies or tetanus vaccinations.

For those patients on stable dosing of prescription sleep medications at entry, downward dose adjustments or discontinuation of treatment may occur during the study.

No more than 1 intra-articular or soft tissue (bursa, tendons, and ligaments) corticosteroid injection is allowed up until the 16-week primary endpoint. After 16 weeks, such injections are permitted.

Any changes to these concomitant medications must be recorded in the Concomitant Therapy of Special Interest eCRF.

Treatment with concomitant therapies for other medical conditions such as diabetes and hypertension is permitted during the study.

7.7.2. Use of Topical Corticosteroids

A washout period of 14 days is required for all TCS prior to randomization at Visit 2.

At baseline (Week 0, Visit 2) and up to Week 104 (Visit 22), patients will receive triamcinolone 0.1% cream (or equivalent-potency TCS) and hydrocortisone 2.5% ointment (or equivalent-potency TCS). See “Choice of Background Topical Corticosteroid” below. Triamcinolone 0.1% cream (moderate-potency TCS) should be applied at least once daily to affected areas until lesions are under control (clear or almost clear). Patients should then switch to hydrocortisone 2.5% ointment (low-potency TCS) and treat previously affected areas once-daily for 7 days and then stop. Hydrocortisone 2.5% ointment (low-potency TCS) may also be used to replace triamcinolone 0.1% cream (moderate-potency TCS) on areas of thin skin (face, neck, folds, and genital areas) and areas with skin atrophy.

If lesions reappear during the course of the study, the patients should resume the once-daily applications of triamcinolone 0.1% cream (moderate-potency TCS) or hydrocortisone 2.5% ointment (low-potency TCS) as described above.

For patients whose lesions persist or worsen despite the use of emollients and low- and/or moderate-potency TCS and/or patients who require daily applications on large surfaces may be considered for topical rescue with high- or ultra-high-potency TCS (see Section 7.7.5 for details).

On the days of study visits, topical therapy including TCS should not be applied before the patient has undergone all study procedures and clinical evaluations in order to allow adequate assessment of skin dryness.

After Week 104, use of TCS may be continued as directed by the investigator, as per clinical practice. Background TCS will no longer be provided nor reimbursed to study participants by the sponsor, unless required by local law.

Choice of Background Topical Corticosteroid

Where possible, triamcinolone cream 0.1% and/or hydrocortisone 2.5% ointment will be supplied by the sponsor for use as background TCS up to Week 104 (Visit 22). In the event of these specific TCS being unavailable, an alternate, equivalent-potency TCS may be provided by the sponsor (see below). Topical corticosteroid use, when supplied by the sponsor, should be recorded via weight of dispensed and returned tubes as indicated in the Schedule of Activities (Section 2). In the event that the sponsor is unable to supply TCS, commercially available triamcinolone 0.1% cream and/or hydrocortisone 2.5% ointment may be supplied by the sites.

- Where providing triamcinolone 0.1% cream and/or hydrocortisone 2.5% ointment is not possible, an equivalent-potency TCS cream and/or ointment that is in line with local practices can be supplied by the sites. Refer to [Appendix 7](#) for guidance on potency equivalence.
- Where possible, TCS use when supplied by the site should also be recorded via weight of dispensed and returned tubes, as indicated in the Schedule of Activities (Section 2); however, where this is not practical, this information does not need to be recorded, and will not be considered a protocol violation.
- If the TCS supplied by the sponsor is not considered suitable for an individual patient, an equivalent-potency TCS cream and/or ointment that is in line with local practices can be supplied by the sites. Refer to [Appendix 7](#) for guidance on potency equivalence.

Choice of High- and Ultra-High-Potency Topical Corticosteroids for Rescue

The use and choice of specific high- or ultra-high-potency TCS for rescue is at the discretion of the investigator and it will not be provided by the sponsor. The weights of dispensed and returned tubes of the high- and ultra-high-potency TCS are not required.

Other Topical Treatments

Investigators may also select to use TCIs and/or crisaborole in countries where approved, in place of TCS. If TCIs or crisaborole are prescribed, use should be limited to problem areas (e.g., face, neck, skin folds, genital areas, etc.).

Use of all topical treatments for AD must be recorded in the CRF.

7.7.3. Use of Antihistamines

Antihistamine ophthalmic preparations are permitted during the study.

During Period 2, nonsedating antihistamines are permitted, including, but not limited to, acrivastine, bilastine, cetirizine, desloratadin, fexofenadine, levocetirizine, loratadine, mizolastine, and rupatadine.

During Period 2, sedating antihistamines, including, but not limited to, alimemazine, chlorphenamine, clemastine, cyproheptadine, diphenhydramine, hydroxyzine, ketotifen, and promethazine, are **not** permitted and will require a 28-day washout prior to randomization.

During Periods 3, 4, and 5, there are no restrictions for antihistamine use; both sedating and nonsedating antihistamines are permitted.

7.7.4. Prohibited Medications and Procedures

Prohibited Medications and Procedures Not Requiring Urgent Interruption of Investigational Product

The following therapies will not be allowed during the course of the study and, if taken by or administered to the patient, the prohibited therapy must be discontinued. If the patient is not able to discontinue use of the following then investigational product will be permanently discontinued.

- topical antihistamines or sedating, systemic antihistamines in Period 2 (see Section 7.7.3, Use of Antihistamines, for additional information).
- self-treatment with tanning booth
- bleach baths (swimming in chlorinated pools is permitted)

Prohibited Medications and Procedures Requiring Temporary Interruption of Investigational Product

The following therapies will not be allowed during the course of the study and, if taken by or administered to the patient, temporary interruption of investigational product is required.

- live vaccines (including Bacillus Calmette-Guérin [BCG] or herpes zoster), (see Exclusion Criterion [29])
 - For BCG vaccination, investigational product should be temporarily interrupted for 12 weeks.
 - For herpes zoster vaccination, investigational product should be temporarily interrupted for 4 weeks.
- systemic corticosteroids for the treatment of an AE (if used for AD see below). Investigational product may be restarted if systemic corticosteroids were used for a short duration (<30 days). If used for >30 days, sponsor approval to restart investigational product is required.
- probenecid: if a patient is inadvertently started on probenecid, investigational product should be temporarily interrupted, and can be resumed after the patient has discontinued probenecid. If a patient is not able to discontinue probenecid, then investigational product should be permanently discontinued.
- phototherapy, including therapeutic phototherapy (psoralen and ultraviolet A, ultraviolet B, excimer laser) as rescue therapy in Period 2 or 3. Investigational product should be temporarily interrupted until completion of the phototherapy.

Prohibited Medications Requiring Permanent Discontinuation of Investigational Product

- any systemic therapy, investigational or commercial (approved or off-label use), used as rescue for the treatment of AD (including systemic corticosteroids, see Section 7.7.5, Rescue Therapy).

- systemic immunosuppressive/immunomodulatory substances, including, but not limited to, cyclosporine, methotrexate, mycophenolate mofetil, interferon- γ , azathioprine, biologic agents, or other JAK inhibitors (e.g., tofacitinib and ruxolitinib).

Note: In the event that these prohibited medications were inadvertently used, agreement and documentation to continue investigational product must be sought from sponsor.

7.7.5. Rescue Therapy

Investigators should make every attempt to conduct efficacy and safety assessments immediately before administering any rescue treatment. An unscheduled visit should be used for this purpose if necessary.

7.7.5.1. Rescue during Period 2: Week 0 (Visit 2) up to Week 52 (Visit 14)

Control of AD symptoms should be attempted by avoiding exacerbating factors, intensifying emollient applications, and using only the permitted study treatments, including background TCS therapy (e.g., triamcinolone 0.1% cream and/or hydrocortisone 2.5% ointment) (see Section [7.7.2](#)).

Rescue with High- and Ultra-High-Potency TCS

Patients whose lesions persist or worsen despite the use of emollients and background TCS therapy (e.g., triamcinolone 0.1% cream and/or hydrocortisone 2.5% ointment) and/or patients who require prolonged applications of triamcinolone 0.1% cream (moderate-potency TCS) on large surfaces may be considered for rescue to high- or ultra-high-potency TCS (see [Appendix 7](#) for TCS potency).

High- or ultra-high-potency TCS may be used once daily for up to 14 consecutive days or based on the maximum duration recommended in the prescribing information.

It is recommended that if a patient reaches “clear” to “almost clear” skin after topical rescue, then high- or ultra-high-potency TCS should be stopped, and low- and/or moderate-potency TCS (e.g., triamcinolone 0.1%, hydrocortisone 2.5% ointment) should be used once daily for an additional 7 days, then stopped.

Patients rescued with high- or ultra-high-potency TCS will continue to take investigational product and use of topical rescue therapy will be documented in the eCRF.

Rescue with Phototherapy

Patients may also be rescued with phototherapy at the discretion of the investigator. Patients rescued with phototherapy will remain in the study and be required to temporarily interrupt use of investigational product until completion of the phototherapy (see Section [8.1.1](#) for Temporary Interruption of Investigational Product).

Rescue with Systemic Therapies

Patients whose disease cannot be controlled by the measures described above may be rescued to systemic therapies (conventional systemics or biologics). These patients will be required to discontinue investigational product and proceed to the ETV before initiating systemic treatment. However, patients rescued to systemic therapies prior to the primary endpoint (Week 16) should be encouraged to continue with study visits and assessments through Visit 8.

7.7.5.2. Rescue during Periods 3 and 4: from Week 52 (Visit 14) to Week 200 (Visit 28)

In Period 3, all patients will continue to use concomitant background TCS (e.g., triamcinolone 0.1% cream and hydrocortisone 2.5% ointment) as described in Section 7.7. In Period 4, use of concomitant may continue as directed by the investigator, as per clinical practice. All patients may be rescued at any time with high- or ultra-high-potency TCS or phototherapy as described in Section 7.7.

As mentioned in Sections 5.1.3 and 5.1.4, patients who reach an IGA ≥ 3 after entry into the randomized downtitration substudy will be automatically retreated with their presubstudy dose of baricitinib.

Patients not eligible for the substudy and who present with an IGA ≥ 3 at Week 52 or anytime thereafter will automatically be rerandomized at a 1:1 ratio to baricitinib 2-mg QD or baricitinib 4-mg QD, but this will only occur once. Patients randomized to baricitinib 4-mg QD at baseline (Week 0, Visit 2) will stay on this dose for the remainder of the trial regardless of IGA.

Patients whose disease cannot be controlled by the measures described above may be rescued to systemic therapies (conventional systemics or biologics). Whenever possible during this Period, it is recommended to wait for at least 4 weeks after the visit at which the patient has reached IGA ≥ 3 to initiate rescue with systemic therapies.

Patients rescued with high- or ultra-high-potency TCS will continue to take investigational product and use of topical rescue therapy will be documented in the eCRF.

Patients rescued with phototherapy will remain in the trial and will be required to temporarily interrupt the use of investigational product until completion of the phototherapy.

Patients who need rescue with systemic therapies (conventional systemics or biologics) during Period 3 will be required to discontinue investigational product and to proceed to the ETV before initiating systemic treatment.

7.8. Treatment after the End of the Study

Period 4 will provide patients who have completed Week 104 visit and have not met criteria for permanent discontinuation, the possibility to remain in the trial for up to 96 additional weeks (up to Week 200) and thus provide patients the opportunity to continue study treatment until the anticipated approval of baricitinib in this indication.

After the conclusion of the study, continued access to baricitinib will not be provided. Patients will be referred to their local treatment centers for AD therapy as clinically indicated.

8. Discontinuation Criteria

8.1. Discontinuation from Study Treatment

8.1.1. Temporary Interruption of Investigational Product

In some circumstances, it may be necessary to temporarily interrupt treatment as a result of AEs or abnormal laboratory values that may have an unclear relationship to investigational product. For example, investigational product should be temporarily interrupted if the patient experiences a cardiovascular AE considered to be related to study treatment, is graded as moderate (Grade 2 according to Common Terminology Criteria for Adverse Events [CTCAE] Version 3.0), and that does not resolve promptly with supportive care. Except in cases of emergency, it is recommended that the investigator consult with Lilly (or its designee) before temporarily interrupting therapy for reasons other than those defined in [Table JAIN.4](#).

For the abnormal laboratory findings and clinical events (regardless of relatedness) listed in [Table JAIN.4](#), specific guidance is provided for temporarily interrupting treatment and when treatment may be restarted. Retest frequency and timing of follow-up laboratory tests to monitor the abnormal finding are at the discretion of the investigator. Investigational product that was temporarily interrupted because of an AE or abnormal laboratory value not specifically covered in [Table JAIN.4](#) may be restarted at the discretion of the investigator.

Table JAIN.4. Medical and Laboratory Criteria for Temporary Interruption of Investigational Product

Hold Investigational Product if the Following Laboratory Test Results or Clinical Events Occur	Investigational Product May Be Resumed When
WBC count <2000 cells/ μ L (<2.00x10 ³ / μ L or <2.00 GI/L)	WBC count \geq 2500 cells/ μ L (\geq 2.50x10 ³ / μ L or \geq 2.50 GI/L)
ANC <1000 cells/ μ L (<1.00x10 ³ / μ L or <1.00 GI/L)	ANC \geq 1200 cells/ μ L (\geq 1.20x10 ³ / μ L or \geq 1.20 GI/L)
Lymphocyte count <500 cells/ μ L (<0.50x10 ³ / μ L or <0.50 GI/L)	Lymphocyte count \geq 750 cells/ μ L (\geq 0.75x10 ³ / μ L or \geq 0.75 GI/L)
Platelet count <75,000/ μ L (<75x10 ³ / μ L or <75 GI/L)	Platelet count \geq 100,000/ μ L (\geq 100x10 ³ / μ L or \geq 100 GI/L)
eGFR <40 mL/min/1.73 m ² (from serum creatinine) for patients with screening eGFR \geq 60 mL/min/1.73 m ²	eGFR \geq 50 mL/min/1.73 m ²
eGFR <30 mL/min/1.73 m ² (from serum creatinine) for patients with screening eGFR \geq 40 to <60 mL/min/1.73 m ²	eGFR \geq 40 mL/min/1.73 m ²
ALT or AST >5 x ULN	ALT and AST return to <2 x ULN, and IP is not considered to be the cause of enzyme elevation
Hemoglobin <8 g/dL (<80.0 g/L)	Hemoglobin \geq 10 g/dL (\geq 100.0 g/L)
Symptomatic herpes zoster	All skin lesions have crusted and are resolving
Infection that, in the opinion of the investigator, merits the IP being interrupted	Resolution of infection

Abbreviations: ALT = alanine aminotransferase; ANC = absolute neutrophil count; AST = aspartate aminotransferase; eGFR = estimated glomerular filtration rate; IP = investigational product; ULN = upper limit of normal; WBC = white blood cell.

Although temporary interruption of investigational product is not a requirement at times of increased potential risk of VTE (e.g., surgery, significant air travel, or other situations involving prolonged immobilization), we recommend following appropriate VTE prophylaxis guidelines to help manage the VTE risk under these circumstances.

For specific guidance on temporary interruption of investigational product after use of a prohibited medication, please refer to Section 7.7.4, Prohibited Medications and Procedures.

Lastly, investigational product should be temporarily interrupted for suicidal ideation or any suicide-related behaviors as assessed by the following patient responses on the C-SSRS:

- A “yes” answer to Question 4 (Active Suicidal Ideation with Some Intent to Act, Without Specific Plan) **or**
- A “yes” answer to Question 5 (Active Suicidal Ideation with Specific Plan and Intent) on the “Suicidal Ideation” portion of the C-SSRS **or**
- A “yes” answer to any of the suicide-related behaviors (actual attempt, interrupted attempt, aborted attempt, preparatory act or behavior) on the “Suicidal Behavior” portion of the C-SSRS.

Note: Prior to resumption of investigational product, it is recommended that a patient be assessed by a psychiatrist or appropriately trained professional to assist in deciding whether the subject should remain on investigational product and ultimately continued participation in the study. A patient does not necessarily have to have investigational product interrupted if they have self-injurious behavior that would be classified as nonsuicidal self-injurious behavior.

8.1.2. Permanent Discontinuation from Investigational Product

Investigational product should be permanently discontinued if the patient is rescued with systemic therapies to treat AD and/or the patient requests to discontinue investigational product.

Discontinuation of the investigational product for abnormal liver tests should be considered by the investigator when a patient meets 1 of the following conditions after consultation with the Lilly-designated medical monitor:

- ALT or AST $>8 \times$ ULN
- ALT or AST $>5 \times$ ULN for more than 2 weeks
- ALT or AST $>3 \times$ ULN and total bilirubin level (TBL) $>2 \times$ ULN or international normalized ratio (INR) >1.5
- ALT or AST $>3 \times$ ULN with the appearance of fatigue, nausea, vomiting, right upper-quadrant pain or tenderness, fever, and/or rash
- ALP $>3 \times$ ULN
- ALP $>2.5 \times$ ULN and TBL $>2 \times$ ULN
- ALP $>2.5 \times$ ULN with the appearance of fatigue, nausea, vomiting, right quadrant pain or tenderness, fever, and/or rash

Note: Patients who are discontinued from investigational product due to a hepatic event or liver test abnormality should have additional hepatic safety data collected via the hepatic safety eCRF.

Investigational product should be permanently discontinued if any of the following laboratory abnormalities are observed:

- white blood cell count <1000 cells/ μ L ($1.00 \times 10^3/\mu$ L or 1.00 GI/L)
- ANC <500 cells/ μ L ($0.50 \times 10^3/\mu$ L or 0.50 GI/L)
- lymphocyte count <200 cells/ μ L ($0.20 \times 10^3/\mu$ L or 0.20 GI/L)
- hemoglobin <6.5 g/dL (<65.0 g/L).

Note: Temporary interruption rules (see Section 8.1.1) must be followed where applicable. For laboratory values that meet permanent discontinuation thresholds, investigational product should be discontinued. However, if in the opinion of the investigator the laboratory abnormality is due to intercurrent illness such as cholelithiasis or another identified factor, laboratory tests may be repeated. Only when the laboratory value meets resumption thresholds (Table JAIN.4) following the resolution of the intercurrent illness or other identified factor may the investigator restart investigational product, after consultation with the Lilly-designated medical monitor.

In addition, patients will be discontinued from investigational product in the following circumstances:

- pregnancy
- malignancy (except for successfully treated basal or squamous cell skin carcinoma)
- hepatitis B virus DNA is detected with a value above limit of quantitation or 2 sequential tests return a value of below the limit of quantitation (see Section 9.4.8).
- certain prohibited medications are taken per Section 7.7.4, Prohibited Medications and Procedures.
- development of a VTE

Note: Patients who develop a VTE may have additional follow up and testing recommended (see Appendix 8).

If a patient discontinues investigational product for any reason, the patient is encouraged to remain in the study through Week 16 (Visit 8) and follow the regular visit schedule to provide the primary efficacy and safety data. Patients discontinuing from the investigational product prematurely for any reason should complete AE and other follow-up procedures per Section 2 (Schedule of Activities), Section 9.2 (Adverse Events), and Section 9.4 (Safety) of this protocol.

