- m For all women of childbearing potential, a serum pregnancy test (central laboratory) will be performed at Visit 1. Urine pregnancy tests (local laboratory) will be performed at Visit 2 and at all subsequent study visits after Visit 3. If required per local regulations and/or institutional guidelines, pregnancy testing can occur at other times during the study treatment period.
- n For female patients ≥ 40 and < 60 years of age who have had a cessation of menses for at least 12 months, an FSH test will be performed to confirm nonchildbearing potential (FSH ≥ 40 mIU/mL).
- o For patients who are positive for HCV antibody, a follow-up test for HCV RNA will be performed automatically. Patients who are positive for HCV antibody and negative for HCV RNA may be enrolled.
- p Patients who are positive for HBcAb and negative for HBV DNA may be enrolled. Any enrolled patient who is HBcAb positive, regardless of HBsAb status or level, must undergo HBV DNA testing per the schedule.
- q Beyond Week 104, low and mid potency TCS will no longer be provided by the sponsor.
- r Only applicable to ET visits and V801 before Period 4.

NOTE: Patients completing V22 and planning to sign the ICF for amendment (e) can participate as long as they have not completed a V801.

3. Introduction

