9.4.8. Hepatitis B Virus DNA Monitoring

Patients who are HBcAb positive and HBV DNA negative (undetectable) at Visit 1 will require periodic measurement of HBV DNA as per study schedule (Section 2), regardless of their hepatitis B surface antibody (HBsAb) status.

The following actions should be taken in response to HBV DNA test results:

- If a single result is obtained with a value “below limit of quantitation,” the test should be repeated within approximately 2 weeks. If the repeat test result is “target not detected,” HBV DNA monitoring will be performed per study schedule (Section 2).
- If the patient has 2 or more test results with a value “below limit of quantitation” or a test result above the limit of quantitation, the patient will be permanently discontinued from investigational product (see Section 8.1.2) and should be referred to a hepatology specialist.

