### **HBV DNA**

A listing of patients with detectable HBV DNA postbaseline will be provided.

HBV DNA status post baseline (not detectable, detectable but not quantifiable [that is, < lower limit of detection (LLOD)], quantifiable [that is,  $\geq$ LLOD]) will be summarized by treatment group stratified by baseline HBV serology status, specifically:

1. HBsAb+ / HBcAb+
2. HBsAb- / HBcAb+

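### The HBV DNA stopping rule is worded differently in Protocol 8.1.2 and 9.4.8, and the SAP's HBV DNA cut-point contradicts its own category names

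*Protocol*

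**What the plan says.** Protocol Section 8.1.2 includes HBV DNA among the circumstances in which investigational product is permanently stopped. The trigger is a "value above limit of quantitation or 2 sequential tests return a value of below the limit of quantitation", and the reader is sent to Section 9.4.8.

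Section 9.4.8 covers patients who were core-antibody positive with undetectable HBV DNA at screening. After one result under the quantitation limit, "the test should be repeated within approximately 2 weeks". If the repeat finds no virus, the patient returns to ordinary scheduled monitoring. The next bullet gives the stopping condition: "If the patient has 2 or more test results with a value “below limit of quantitation” or a test result above the limit of quantitation". Such a patient is permanently taken off investigational product and referred to hepatology. The bullet points back to Section 8.1.2.

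Testing recurs through follow-up. A footnote to the Schedule of Activities says: "Any enrolled patient who is HBcAb positive, regardless of HBsAb status or level, must undergo HBV DNA testing per the schedule". Treatment can last up to 200 weeks.

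SAP Section 6.13.4.6, under HBV DNA, plans a summary of "HBV DNA status post baseline (not detectable, detectable but not quantifiable", and a third, quantifiable category, by treatment group within baseline serology strata. The bracket after the second name gives results below the lower limit of detection (LLOD). The bracket after the third gives results at or above the LLOD. The same subsection also plans a listing of every patient with detectable HBV DNA after baseline.

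**The concern.** Stopping is mandatory here and not left to the investigator's judgment, so the wording has to give one answer for a given series of results. It does not. Two sites with identical results could act differently, each following a section of the protocol.

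The choice also carries into the analysis. Under SAP Section 6.3 the primary and secondary censoring rules both cut efficacy data at permanent study drug discontinuation. Under Section 6.13.1 both safety censoring rules exclude events after it. Which section a site follows therefore decides which of that patient's later data count.

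The SAP wording is a separate matter in the same area. The protocol acts on results below the limit of quantitation and uses no limit of detection as a cut-point. A table cut at the limit of detection could not be matched to the discontinuations that the protocol requires.

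**Working it through.** No power or error-rate calculation applies, and the plan gives no figure to reproduce. The check compares wording, with a count of the result series on which the two rules disagree.

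**Inputs.** Code each test as T (target not detected), B (below the limit of quantitation) or Q (above it).

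- Protocol 8.1.2: stop if there is any Q, or two adjacent Bs.
- Protocol 9.4.8, read literally: stop if there is any Q, or at least two Bs anywhere.

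**Count.** A series of n tests has 3^n possible forms. Any series with a Q stops under both rules, so disagreement can occur only among series of Ts and Bs. The rules disagree where there are at least two Bs but no two adjacent. That number is (T/B series with no adjacent Bs) − (1 + n), where 1 + n counts the series with no B or one B.

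| n | All series | Stop under 8.1.2 | Stop under 9.4.8 | Differ |
|---|---|---|---|---|
| 2 | 9 | 6 | 6 | 3 − 3 = 0 |
| 3 | 27 | 22 | 23 | 5 − 4 = 1 |
| 4 | 81 | 73 | 76 | 8 − 5 = 3 |
| 5 | 243 | 230 | 237 | 13 − 6 = 7 |

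At three tests the one differing series is B-T-B. At four tests they are T-B-T-B, B-T-T-B and B-T-B-T. In every differing series it is 9.4.8 that stops treatment. These are counts of possible series, not probabilities.

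B-T-B is the path that 9.4.8 itself sets up: a low-level result, a negative repeat, a return to the schedule, and another low-level result later. Some series counted as agreement differ in timing. In B-T-B-B, 9.4.8 stops at the third test and 8.1.2 at the fourth, which is about 2 weeks later if the fourth is the required repeat.

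**SAP categories.** Assume only that the limit of detection lies below the limit of quantitation.

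| Result | Protocol term | SAP category by name | SAP category by bracket |
|---|---|---|---|
| Not detected | Target not detected | Not detectable | Not detectable, or the middle category if only the below-LLOD condition is coded |
| Detected, under the quantitation limit | Below quantitation | Detectable but not quantifiable | Quantifiable (at or above LLOD) |
| Over the quantitation limit | Above quantitation | Quantifiable | Quantifiable |

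A result below the limit of detection is not detectable, so no result satisfies both the name and the bracket of the middle category. The second row is where name and bracket assign different categories.

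**The case against.** The best defence of the protocol is that the two sections cite each other and were probably meant as one rule. The bullets in 9.4.8 can be read as a sequence: a single low-level result leads to a repeat, a negative repeat ends the episode, and the stopping bullet then covers a repeat that is also below quantitation. On that reading two or more means the test and its repeat, which matches 8.1.2. A later isolated result would be a new single result needing its own repeat. This is a fair reading, and it makes the defect as much an ambiguity as a conflict between two settled rules. A reader might infer the latter, but the documents do not establish it. Nor do they state the reconciling reading: nothing says that a cleared result drops out of the count.

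For the SAP, the category names are right and correspond one to one with the results that 9.4.8 describes. Only the bracketed limit is wrong, and it is probably a slip. If results are tabulated by the reported category, the bracket may never be used. A reader might infer that every low-level result will be misclassified, or that such cases are hidden. Neither is supported: misclassification follows only if the bracket is programmed over the name, and the planned listing would still show each patient with detectable DNA. The wrong limit does appear in both brackets, however, and a programmer could follow it.

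It is also tempting to attach a percentage of patients to the protocol discrepancy. That would need a per-test chance of a low-level result, an assumption about dependence between tests, the number of tests actually done and the outcome of the repeats. The documents give no per-test chance. The number of tests varies because Period 4 is optional, and the SAP revision history reports phased site closure. That closure also limits what a protocol clarification can still achieve prospectively.

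**Conclusion.** Wrong as written, on two narrow points. First, 8.1.2 and 9.4.8 do not state the same below-quantitation criterion for a mandatory stop. Read literally, they give different answers when a below-quantitation result, a negative repeat and a later below-quantitation result occur in turn. The above-quantitation trigger is the same in both, and no other section resolves the difference. Second, the bracketed limits in SAP 6.13.4.6 contradict the category names beside them and the protocol's cut-point.

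The size cannot be computed. Only core-antibody-positive patients are exposed, and neither their number nor their rate of low-level results is given. The SAP effect is confined to a descriptive safety table and is conditional on the brackets being programmed. Sample size, alpha and the primary efficacy analysis are not affected. The case for acting is that a safety rule should have one reading, and that the corrections are small.

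**What to change.** Reconcile Protocol Sections 8.1.2 and 9.4.8 so that the same rule stands in both. The rule should say explicitly whether a below-quantitation result followed by a negative repeat still counts toward a later one. Which rule is intended is for the sponsor to decide; no choice between them is proposed here. The cost is a clarification letter or a line of amendment wording.

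In SAP Section 6.13.4.6, replace the limit of detection in both brackets with the lower limit of quantitation (LLOQ), giving three categories: not detected; detected but below LLOQ; at or above LLOQ. The cost is one table definition, with no new data.

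Because sites are closing, it is also worth searching the existing HBV DNA results for the below, not detected, below pattern and reporting what was done with any such patient.
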